11. POTENTIAL BENEFITS TO SUBJECTS

Parents and caregivers may not experience any direct benefits from participating in this study. However, participants in prior FASD research studies at MHFC have commented on how they value and derive personal satisfaction in participating in research to increase knowledge about this under-recognized condition and effective strategies to benefit other children and families. It is also possible, although not guaranteed, that participants might derive benefit from receiving the FMF Connect program. Possible benefits may include increased knowledge about FASD and parenting strategies or social support from other caregivers.

12. COSTS FOR PARTICIPATION

There are no costs to participate.

13. PAYMENT FOR PARTICIPATION

Eligible parents/caregivers will receive a reloadable gift card associated with the Advarra system. They will receive \$40 on the gift card for completing T1 and T3 surveys, and a \$20 for completing the briefer T2 surveys.

14. SUBJECT WITHDRAWALS

Subjects will be advised during the consent process that they have the right to withdraw from the study at any time without prejudice. They can choose to use the app as much as they want (or not at all). We are interested in obtaining survey data as well as feedback about the user experience from as many participants as possible, including those who chose not to use the app or found it hard to

navigate. This information is useful in identifying ways to improve the app and facilitate user engagement. Subjects can choose not to complete any or all of the study assessments. They can also completely withdraw from the study with no future contact if they choose. In this case, any data they have previously provided may be used in analyses.

15. PRIVACY AND CONFIDENTIALITY OF SUBJECTS AND RESEARCH DATA

All data will be used solely for research purposes and will be securely locked in designated file cabinets, secure data servers at MHFC, Project REDCap database, and an encrypted, HIPAA-complaint Cloud database (for data collected via the app; see above). Identifying information will be stored separately from other data, which will be stored by research ID number. Multiple procedures will be implemented to protect participant data collected through the app, which are further detailed in the section “Protections Against Risks.” Only senior key personnel and project research staff will have access to the data.

Consistent with the mission of CIFASD, the CIFASD Data Repository allows for data sharing for internal CIFASD investigators across projects as well approved external investigators. A CIFASD Data Sharing Policy has been established and is available on the CIFASD website: <https://cifasd.org/data-sharing/>. External investigators need to submit a CIFASD Data Access Request Form, CIFASD Data Use Agreement, and provide documentation of IRB approval.

17. DATA / SAMPLE STORAGE FOR FUTURE USE

As a CIFASD project, de-identified data from this project will be stored indefinitely in the CIFASD Central Repository, as required by CIFASD and NIAAA. The Central Repository is hosted and managed at Indiana University. Policies and procedures associated with the CIFASD Central repository are described in the prior section. Also, since data are associated with a GUID they can be aggregated with other studies with overlapping participants.

All data (de-identified and identifying) will be securely stored locally for an indefinite period. De-identified and identifying information will be stored separately as detailed above. Novel research questions may arise in the future that this important dataset could answer. Future studies may also be interested in long-term follow-up of families who participated in this research. Retaining identifying information would facilitate contacting families (subsequent to new IRB approval) to see if they would be interested in participating in follow-up research. MHFC has well-established data security procedures in place for long-term storage and maintenance of data. Only approved project staff will have access to data.

18. DATA AND SAFETY MONITORING PLAN

Because the research involves the provision of a mobile health parenting intervention for parents and caregivers, the risk for a serious adverse event due to provision of the intervention is low. Adverse events that could occur in children with FASD or their parents/caregivers could include aggression or violence towards others, maltreatment, self-harm or suicidality, or the need for inpatient hospitalization. However, these occurrences are unlikely to be a direct consequence of participation in the proposed research or interventions.

[name] will assume ultimate responsibility for the safety and well-being of research participants and the integrity of data collected. [name] has conducted several RCTs pilot feasibility studies with children and teens with FASD and their families. She is a licensed psychologist in the state of New York and is involved in other clinical and research activities at MHFC where maltreatment and suicidality are commonly reported.

The well-being of participants will be monitored throughout the course of the proposed research. If there are concerns regarding a participant during interactions with research staff, staff will immediately contact [name] for consultation and a plan will be developed to address the concerns raised.

Coaches and Peer Moderators will be trained to contact [name] immediately about any significant concerns that arise during their interactions with participants in the app. Additionally, because MHFC provides other treatment programs, there are other back-up clinical supervisors available for consultation for immediate needs. A phone tree will be established, similar to other projects at MHFC, and will be provided to Coaches and Peer Moderators. [name] will meet with Coaches weekly to provide supervision and will assess participant well-being. [name] will also provide supervision to Peer Moderators; the frequency of these meetings will depend on the activity level with the Family Forum (during prior beta-test and feasibility trials some weeks had only a few new posts), but will occur at minimum every 3 weeks. [name] will consult with other co-Investigators and clinical staff at MHFC, as appropriate, to address participant well-being concerns.

An independent safety monitoring board has also been established for the larger project, consisting of researchers and clinicians with relevant expertise with at-risk populations, clinical trial monitoring, and human subjects protections and technology. ISM members and their areas of expertise are listed in the following table:

Name	Title & Affiliation	Relevant Areas of Expertise & Experience
[name].	Director & Professor, Mt. Hope Family Center, University of Rochester	Clinical psychologist; developmental psychopathology; relational interventions; maternal depression; maltreatment; prevention of teen depression; has conducted multiple large-scale intervention trials with high-risk populations.
[name], M.S. PNP	Clinical Director, Kirch Developmental Services Center, Neurodevelopmental and Behavioral Pediatrics, University of Rochester Medical Center	Pediatric nurse practitioner; physical and mental health of children with developmental disabilities; intellectual disability, FASD, autism, and cerebral palsy.
[name].	Associate Professor in Psychiatry and Pediatrics, Center for the Study and Prevention of Suicide, University of Rochester Medical Center	Clinical psychologist; suicide prevention; public health messaging; safe and ethical use of technology in prevention science

The ISM committee will review and suggest modifications to research protocols and consent documents to assure scientific integrity and adherence to human subjects’ protection policies. They will meet with the PI and co-Investigators twice a year to monitor safety issues and provide feedback on scientific and ethical issues relating to project implementation. The IRB will be notified immediately of any adverse events via telephone and submission of a “University of Rochester Serious Adverse Event Report”. Such events would also be reported to NIAAA. The proximity of committee members will also facilitate their ability to monitor data management activities. The committee may ask to review data for quality control purposes.

Ethically, we are committed to ensuring the welfare of children and their families. Any significant mental health or safety issues detected during the conduct of this investigation will be discussed with participants and options for the receipt of services presented. The FMF Connect app will also contain a module with links for mental health and crisis resources, as an additional safeguard. A safety message will also be included in the app to direct caregivers to call 9-1-1 or other local crisis services in the event of an emergency.

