4. STUDY DESIGN

This study involves a three arm RCT with equal allocation to the following conditions: (1) FMF Connect + coaching, (2) FMF Connect alone, and (3) waitlist control. Quantitative survey data will be collected at three timepoints: baseline (T1), 6-weeks (T2), and 12-weeks (T3). The T2 timepoint will involve an abbreviated battery designed to allow statistical tests of mediation hypotheses (see Data Analysis Plan below). Primary study outcomes include child behavior, parent FASD knowledge,

parenting self-efficacy, behavior attributions, family needs met, and parent use of self-care. We are also interested in participant ratings of app quality and patterns of app usage. App usage will be recorded through AWS during the study period. After T3, study participants in the waitlist control group will receive the FMF Connect app.

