5. SUBJECT POPULATION

The subject population will include parents and caregivers of children (ages 3-12) with fetal alcohol spectrum disorders (FASD) or affected by prenatal alcohol exposure (PAE) who live in the United States.

We are aiming to include 150 parents or caregivers with usable data in this study to achieve adequate power for study aims (see data analysis section below). We expect a portion of families will enroll in the study, but not complete assessments or install the app. Based on our feasibility trial, 57% of participants who initiated screening were eligible for the study and had complete data. This percentage may be a bit lower than we can achieve for the proposed RCT given that the COVID-19 pandemic began right after the initiation of the feasibility trial and affected participation. We also identified some inefficiencies in our enrollment process that we can improve to reduce incomplete data. Of eligible families selected for the study, we expect about 85% of eligible families to complete baseline surveys. Of these families, about 80% are likely to install and use the app at least once. To attain our desired sample size, we will aim to enroll about 300 parents and caregivers.

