9. STUDY PROCEDURES

Data Collection & Randomization Procedures

Parents/caregivers who are eligible for the study will be sent an email inviting them to complete the baseline study surveys (see survey battery below) administered by REDCap. Participants will be

asked to enter their zip code to verify their identity when completing baseline and follow-up surveys (this will be verified against value entered in demographic surveys in the screening module). Families deemed ineligible after detailed review will be informed of their status.

Following baseline survey completion, participants will be randomized to one of three arms of the RCT:

1. FMF Connect app + text based coaching (within the app)
2. FMF Connect app (without coaching)
3. Waitlist control

Randomization will occur through the REDCap Randomization module, with an equal allocation pattern across groups. Participants will be notified of their group status via email. Emails for parents/caregivers in either of the FMF Connect app intervention groups (groups 1 and 2) will also include instructions of how to install the FMF Connect app on their devices. The email for the parents/caregivers in the FMF Connect app + coaching group (group 1) will inform them that they will receive an introductory email from their assigned coach in the next few days. Details about the FMF Connect app and Coaching interventions and described below.

All participants regardless of group assignment will receive emails through REDCap at 6 weeks and 12 weeks inviting them to complete follow-up surveys, along with a personalized link (see survey battery below). The assessment battery is estimated to take 35-45 minutes to complete at T1 and T3; T2 is estimated at 15-20 min. Waitlist control participants will receive the FMF Connect app following T3 survey completion.

Measure	Baseline (T1)	6-Weeks (T2)	12-Weeks (T3)
Eyberg Child Behavior Inventory (5-8min)	X		X
Reasons for Children’s Behavior Scale (4-6min)	X	X	X
Everyday Life Scale (4-6min)	X	X	X
Parenting Sense of Competence Scale (3-5min)	X	X	X
Family Needs Questionnaire (3-5min)	X		X
Knowledge & Advocacy Questionnaire (15-20min)	X		X
Self-Care and Support Assessment (3-5min)	X		X
Adverse Childhood Experiences (2 min)	X		
Family Background & Services Survey (5-10min)	X		X
COVID-19 Experiences Survey (5 min)			X
User Version of the Mobile Health Application Rating Scale (5-8min)			X

FMF Connect mHealth Intervention

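### In the supplied text, the crisis links and emergency message reach participants only through the app, which the waitlist third does not receive until after T3

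*Combined protocol and SAP*

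**What the plan says.** Section 18 (Data and Safety Monitoring Plan) describes two standing sources of safety information, both inside the app. On the first it says: "The FMF Connect app will also contain a module with links for mental health and crisis resources, as an additional safeguard". On the second: "A safety message will also be included in the app to direct caregivers to call 9-1-1 or other local crisis services".

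The same section states whom the risks concern: "Adverse events that could occur in children with FASD or their parents/caregivers could include aggression or violence towards others". It goes on to list maltreatment, self-harm or suicidality, and inpatient hospitalisation. It considers these events unlikely to result directly from taking part. Nothing in the list is limited by arm.

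On who has the app and when, Section 4 says "This study involves a three arm RCT with equal allocation to the following conditions", one of which is the waitlist. Section 9 says "Waitlist control participants will receive the FMF Connect app following T3 survey completion". Section 5 expects incomplete uptake among families who finish baseline: "Of these families, about 80% are likely to install and use the app at least once".

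Section 18 also has protections that do not depend on the app. Well-being is monitored throughout, staff escalate concerns that arise in their dealings with participants, and significant problems that come to light are discussed with the participant and service options offered.

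**The concern.** The sponsor judged crisis links and an emergency message worth giving, and did so for risks that it attributes to the population and not to the app. The delivery route is narrower than that reasoning: it follows the intervention, so one randomised arm does not get the information during the comparison period.

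The waitlist arm is also the arm with the least described human contact. After randomisation, Section 9 schedules only e-mails and online surveys for it. Coaches and peer moderators, who are trained to raise concerns, meet participants only inside the app. All arms complete an adverse childhood experiences form at T1, and child-behaviour and self-care forms at T1 and T3. The supplied text describes no resource text accompanying those surveys.

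What is at stake is participant welfare. No estimate, power figure or planned analysis in Section 19 depends on this.

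**Working it through.** The plan states no figure for the share of participants without these items, so there is none to reproduce. The check sets the sections side by side and adds simple arithmetic.

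1. **Route.** Crisis links: in the app (Section 18). Emergency message: in the app (Section 18). Section 9 describes the survey invitations and group-assignment e-mails and mentions neither item. No other supplied section gives a second route.

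2. **Who is randomised.** "Following baseline survey completion, participants will be randomized to one of three arms of the RCT". The randomised set is therefore the baseline completers.

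3. **Share without access by design.** With three equal arms, the waitlist share is 1/3 = 33.3%, whatever the total.
   - If 150 are randomised: 150 / 3 = 50.
   - If the 300 of Section 5 are taken as eligible families (an assumption, since that section does not clearly say so) and its 85% baseline completion applies: 300 × 0.85 = 255 randomised, and 255 / 3 = 85.

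4. **Duration.** From randomisation after T1 until T3 is completed: about 12 weeks.

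5. **Families offered the app who may not open it.** Section 5 implies about 1 − 0.80 = 20% of those offered it. The two app arms are 2/3 of those randomised, so this is 2/3 × 0.20 = 13.3% of all randomised (20 of 150, or 34 of 255). These families can open the app at any time, so they are counted separately from step 3.

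6. **What still covers the waitlist arm.**

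| Protection | Covers the waitlist arm before T3? |
|---|---|
| Crisis links in the app | No |
| Emergency message in the app | No |
| Coaches and peer moderators alerting the investigator | No, works through the app |
| Staff escalation during interactions | Yes, but scheduled contact is e-mail and online surveys |
| Discussion of detected problems, with service options | Yes, if a problem is detected |
| Safety board meeting twice a year | Yes, as oversight and not as a participant resource |
| Usual community care (Section 10) | Yes |

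**The case against.** The strongest reply is that the main safeguard already covers everyone. The commitment to discuss detected problems has no arm restriction, monitoring runs throughout, participants see the coordinator's contact details at consent (Section 8), may skip questions (Section 10), and keep their usual care. The module is expressly an extra. Placing it in the app also has a rationale, because the app adds forum and coach interaction, and Section 10 names the forum as a source of discomfort. No section contradicts another. All of this stands, and it limits the point to a gap in an additional layer. It does not remove the point, because the events listed in Section 18 are not attributed to app use.

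A reader might infer more in four ways, none of which the documents support.

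- **That nearly half lack the safeguard.** Adding steps 3 and 5 gives 33.3% + 13.3% = 46.7% (53.3% to 40.0% if uptake were assumed to be 70% to 90%). This pools families who cannot open the app with families who are offered it and, under Section 14, may use it as much or as little as they like. Only the waitlist third is without access by design.
- **That the arm comparison is confounded.** The module is part of the app and so of the randomised package; a component of the assigned intervention does not confound its comparison with waitlist. Crisis events are not among the outcomes in Section 4, and Section 19 plans no analysis of them. A services survey is collected at T1 and T3, but no comparison of service use is planned.
- **That the resources exist nowhere else.** Consent pages were removed from the supplied text, and the survey pages and e-mail templates are not reproduced. Absence is shown only for the text supplied.
- **That waitlist families are unprotected.** The last four rows of the table say otherwise.

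**Conclusion.** The point holds in limited form. On the supplied text, two safeguards that the sponsor considered worth providing do not reach the waitlist arm, one third of those randomised, for about 12 weeks, although the named events can occur in every arm. About 20% of families offered the app may also never open it, but that is non-uptake and not withheld access.

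The one-third share rests on equal allocation and on the app being withheld until after T3, both of which are stated. The claim that there is no other route rests on the supplied text and would fall if the consent, survey or e-mail pages already carry the same information. That the waitlist arm has little other contact is a reading of the schedule in Section 9; the documents do not quantify contact by arm.

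This is an inexpensive improvement to participant protection. It reveals no error in the design or analysis and has no bearing on the validity of the trial's results.

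**What to change.** Place the resource links and safety message prepared for the app on the closing pages of the T1, T2 and T3 REDCap surveys and in the group-assignment e-mail for all three arms. The T1 page precedes randomisation, so it reaches every participant before arms are assigned, and the later pages and the e-mail also reach families who never install the app.

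Amend Section 18 to say that this safeguard covers all participants. If the consent or survey pages already carry the text, it is enough for Section 18 to say so.

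The cost is an IRB modification and copying prepared text into survey pages and e-mail templates. The downside is that a small amount of generic resource information reaches the waitlist arm. It is not FASD education or skills content, so any effect on the contrast between arms should be negligible.

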19. DATA ANALYSIS PLAN

Aim 1: For the two intervention groups, compare patterns of app usage (i.e., frequency, duration, use of core components) that relate to greater improvements in child and caregiver outcomes. Assess whether FMF Connect + Coaching results in higher usage of the app relative to FMF Connect alone.

A series of Multiple Regression analyses will test how app usage (i.e., frequency, duration, content/components accessed) relates to change in outcomes (i.e., parenting efficacy, FASD knowledge, family needs, child behavior) over time, controlling for pre-intervention level of functioning. With a sample size of 100 (n=50 per intervention group) and assuming $\alpha = .05$, there will be power .80 to detect small/medium effects ($f^2=.10$), .94 to detect medium effects ($f^2=.15$), and power $> .99$ to detect large effects ($f^2=.35$).

Aim 2: Examine whether families randomized to the three study arms differ in outcomes.

Repeated Measures Analysis of Variance will test whether families randomized to FMF Connect groups demonstrate improved outcomes relative to the waitlist group at 12 weeks. Pairwise comparisons will test for differences among intervention groups to determine if coaching adds additional benefit. Assuming a correlation among repeated measures ranging from .3 to .5 ($\alpha = .05$), with a sample of 150 and 3 time points, there will be power between .87-.96 to detect a small/medium effect ($f=.175$) and $>.99$ to detect medium and large effects ($f=.25$ and $f=.40$).

Aim 3: Examine whether parental attributions of child misbehavior mediate intervention-related changes in parenting efficacy and child behavior.

Mediation analyses will test whether parental attribution mediates the effects of FMF Connect on parenting efficacy and child behavior, including baseline levels of the respective outcomes. Given a sample size of 150, there will be adequate power ($>.80$) to detect small/medium effects within the mediation models using the bias-corrected bootstrap method.

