1. PURPOSE OF STUDY

This study represents the third phase of a larger research project developed for a U01 award as part of the Collaborative Initiative on Fetal Alcohol Spectrum Disorders (CIFASD) funded by the National Institute on Alcohol Abuse and Alcoholism (NIAAA). The overall project aims to develop and evaluate a mobile health (mHealth) application (app) for parents/caregivers of children with fetal alcohol spectrum disorders (FASD). The primary focus of the FMF Connect app is to provide parent/caregiver education and support.

The first phase of this project was approved under IRB protocol #1266 (legacy RSRB#67394). In that phase we used qualitative research methods to engage parents and caregivers in the development of the mHealth intervention and obtain iterative feedback on acceptability and feasibility. A prototype of the app was developed in both iOS and Android and beta-testing was completed with parents/caregivers and providers. In the second phase of the study, we conducted a feasibility trial of the FMF Connect app with parents/caregivers under IRB protocol #4433. This included quantitative pre-post surveys and qualitative interviews with a subsample of users to optimize the intervention and trial procedures. In this third phase, we will conduct a larger scale randomized controlled trial (RCT) to test the efficacy of the FMF Connect app for parents/caregivers of children with FASD. We hypothesize that participants who receive the FMF Connect app (with or without the additional Coaching Module) will have improve outcomes relative to the waitlist control group. We anticipate the Coaching Module will increase participant engagement and usage of the FMF Connect app. Finally, we hypothesize that parental attributions of behavior targeted by the FMF Connect app will mediate intervention effects on child behavior and parenting self-efficacy.

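### The Aim 1 usage-outcome regressions pool coached and uncoached families without naming an arm term, so part of any direct coaching effect on outcomes would be attributed to app usage

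*Combined protocol and SAP*

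**What the plan says.** Section 19, Aim 1, covers the two intervention groups. The method is given as: "A series of Multiple Regression analyses will test how app usage", in terms of frequency, duration and content used, is related to change in outcomes. The adjustment named is "controlling for pre-intervention level of functioning". The power statement pools the arms: "With a sample size of 100 (n=50 per intervention group". No arm covariate, usage-by-arm interaction or within-arm analysis is mentioned for these regressions.

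Three other places bear on the point:
- Section 1 states a direction for coaching and usage: "We anticipate the Coaching Module will increase participant engagement and usage of the FMF Connect app".
- Section 9, Coaching Module, describes individually tailored messages, support for the family's own goals, and motivational interviewing by trained coaches.
- Section 19, Aim 2, leaves open whether coaching affects outcomes: "Pairwise comparisons will test for differences among intervention groups to determine if coaching adds additional benefit". That comparison does not involve usage.

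Aim 1 also asks whether coaching raises usage. There usage is the outcome, so that analysis does not adjust the usage-outcome slope.

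**The concern.** Arm is randomised and is expected to shift usage. If coaching also changes outcomes by a route other than usage, arm is a common cause of both variables in the pooled regression. The pooled slope then mixes two things: the association between usage and outcome among families treated alike, and the difference between the coached and uncoached groups.

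Aim 1 is meant to show which patterns of app use go with greater improvement. A slope that partly reflects contact with a coach would point to app features when the benefit came from the coach. Adjusting for the baseline outcome does not help, because randomisation makes baseline independent of arm in expectation.

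**Working it through.** **1. The plan's own power figure.** Inputs from section 19: N=100, alpha .05, f² of .10, .15 and .35. Use the noncentral F test with noncentrality f²N and degrees of freedom (u, N−k−1), where u is the number of tested predictors and k the total number.
- u=2, k=2: .803, .937, >.99. This matches the stated .80, .94, >.99.
- u=1 gives .88 and .97, and u=3 gives .74 and .91, for the first two effect sizes. Neither matches.

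The stated power therefore rests on two tested predictors, which the plan does not identify.

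**2. The spurious slope.** Code arm C as 0/1 with equal allocation, so its variance is .25. Let usage U = gC + noise and outcome Y = dC + r × baseline + noise, each with within-arm SD 1 and no usage effect on Y. Leaving C out gives a slope on U of

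cov(U,Y)/var(U) = .25gd/(1+.25g²).

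The share of d that loads on the slope, per within-arm SD of usage, is .25g/(1+.25g²):
- g=0.3: .075/1.0225 = 7%
- g=0.5: .125/1.0625 = 12%
- g=0.8: .200/1.16 = 17%

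If g=0 or d=0 the slope is zero.

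**3. The false-positive rate.** The values of g and d, and a baseline correlation r of .5 or .7, are assumptions; the documents give none of them. One cell by hand, with g=d=0.5 and r=.5:
- slope = .0625/1.0625 = .0588
- residual variance = (1−r²) + .25d²/(1+.25g²) = .75 + .0588 = .8088
- standard error = √.8088/(√100 × √1.0625) = .0872
- ratio = .0588/.0872 = .67
- two-sided rejection at 1.96 is about 10%, against a nominal 5%.

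The other cells follow the same way. The last two columns are from simulation with 50 families per arm and at least 4,000 replicates per cell.

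| g / d (SD) | Spurious slope | Normal approximation, r=.5 / .7 | Simulated, no arm term | Simulated, arm term |
|---|---|---|---|---|
| 0.3 / 0.2 | .015 | 5% / 5% | 5%-6% | about 5% |
| 0.5 / 0.35 | .041 | 8% / 9% | 7%-9% | about 5% |
| 0.5 / 0.5 | .059 | 10% / 13% | 10%-13% | about 5% |
| 0.8 / 0.5 | .086 | 18% / 24% | 17%-23% | about 5% |

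With the arm term the mean usage coefficient is about zero in every simulated cell.

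**4. Power after the change.** With u=2 and k=4 (two usage predictors, baseline, arm), power is .802, .937 and >.99 with noncentrality f²N. With noncentrality f²(u+v+1), where v=95, it is .794, .932 and >.99.

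**The case against.** **The plan is silent; it does not exclude arm.** This stands. The plan is short, and the unidentified second tested predictor in the power calculation could be another usage measure or could be arm. The point is about the plan as written: only baseline is named, and an analyst who follows it would leave arm out.

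**A path outside usage is not a hypothesis of the plan.** This also stands. Section 1 hypothesises that coaching raises usage, and its outcome hypothesis sets the app, with or without coaching, against waitlist. Section 9 describes coaching as support for continued use and goal setting inside the app. If coaching works only through usage, d=0 and omitting arm causes no bias. A reader might infer that the plan's own hypotheses make arm a confounder. They supply the arm-to-usage path only. The direct path is plausible from the coaching content but remains an assumption.

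**The slopes are small.** They run from .015 to .086, against a partial correlation of about .30 implied by f²=.10 (√(.10/1.10)), the smallest effect for which the plan gives power. That is fair as to slope size. It does not remove the inflated error rate when both coaching effects are moderate.

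**Two stronger readings do not hold.** A reader might infer that all of a direct coaching effect is credited to usage. Only 7%-17% of it is, over the range of g shown. A reader might also infer that the bias has the same sign in every usage-by-outcome regression, so that the series would seem mutually confirming. That would need coaching to raise every usage measure and directly improve every outcome. Coaching could, for example, substitute for Family Forum use, and the calculation covers one usage measure and one outcome.

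**An arm term leaves self-selected usage untouched.** This is correct. The 5% rate with an arm term holds only because the calculation includes no within-arm confounding.

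**Conclusion.** The point holds in a limited form. As written, the Aim 1 regressions leave the usage slope open to bias from coaching whenever coaching both shifts usage, as the plan expects, and affects outcomes by another route, as its content makes possible. The consequence ranges from negligible at small effects (5%-6% false positives at 0.3/0.2 SD) to substantial when both are moderate or large (17%-23% at 0.8/0.5 SD). These figures rest on assumed coaching effects and baseline correlations, on a true usage association of zero, and on one usage measure tested at two-sided .05. Aim 2's randomised comparisons are not affected. The case for acting is that an avoidable bias in a stated aim can be removed at almost no cost.

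**What to change.** In section 19, Aim 1, state that every usage-outcome regression includes randomised arm (coaching versus app alone) as a covariate alongside the baseline value, and that the arm-adjusted usage slope is the one reported. Continue to describe it as an association, because families choose how much to use the app within each arm.

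This is a free improvement: one line of text, one degree of freedom and no new data. The usage variance that lies between arms no longer contributes, about 6% at a 0.5 SD shift (.0625/1.0625). Power at the plan's stated effect sizes stays at about .80, .94 and >.99. Writing it in before analysis also keeps the choice of covariates from being made after results are seen.
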